9.2. Adverse Events

An AE is defined as any untoward medical occurrence in a participant enrolled into this study regardless of its causal relationship to study drug.

A treatment-emergent AE (TEAE) is defined as any event not present before exposure to study drug or any event already present that worsens in either intensity or frequency after exposure to study drug.

A serious adverse event (SAE) is defined as any event that:

- results in death,
- is immediately life threatening,

- requires in-participant hospitalization or prolongation of existing hospitalization,
- results in persistent or significant disability/incapacity, or
- is a congenital anomaly/birth defect.
- Important medical events that may not result in death, be life threatening, or require hospitalization may be considered SAEs when, based upon appropriate medical judgment, they may jeopardize the participant or may require medical or surgical intervention to prevent one of the outcomes listed in this definition.

Hospitalization does not include admissions for treatment of a pre-existing condition, including surgery, not associated with a new AE; respite care; social reasons; administrative reasons; skilled nursing care; rehabilitation; hospice; or same-day surgery.

All AEs, TEAEs, and SAEs will be coded using the MedDRA dictionary (v24.0 March 2021).

The causality to treatment will be grouped into three categories for the summaries: not related (reported as either "not related" or "unlikely related"), possibly related (reported as "possible related"), and related (reported as either "probably related", "definitely related", or missing causality)

For Part 1 and Part 2 the number and percent of participants reporting TEAEs, grouped by MedDRA system organ class and preferred term, will be tabulated by treatment group (treatment cohort for Part 2) and causality to treatment (total, not related, possibly related, or related). In the case of multiple occurrences of the same TEAE within the same participant, the most related one will be counted for the participant. This summary will be repeated for the common TEAEs defined as the incidence rate of $\geq 3\%$ at the lixivaptan group in Part 1.

The number and percent of participants reporting TEAEs, grouped by MedDRA system organ class and preferred term, will be tabulated by severity and treatment group (treatment cohort for Part 2) for all the TEAEs. In the case of multiple occurrences of the same TEAE within the same participant, the most severe one will be counted.

Adverse event summaries, grouping by MedDRA system organ class and preferred term, will be repeated by severity and treatment group (treatment cohort for Part 2) for treatment related TEAEs including possibly related TEAEs.

An overall summary of TEAEs will be presented by treatment group. The overall summary will include the total number and percent of participants reporting:

- Any TEAEs
- Any treatment-related TEAE
- Any severe TEAE
- Any severe treatment-related TEAE
- Any serious TEAE

- Any serious treatment-related TEAE
- Any TEAE of special interest (TEAESI)
- Any TEAE leading to permanent study drug discontinuation
- TEAEs resulting in death

In the AE data listings, all AEs will be displayed to include whether the adverse events are SAEs, AESIs, date of AEs, relationship to study drug, severity, and action taken. AEs that are not treatment-emergent will be flagged.

9.2.1. Adverse Events Leading to Study Drug Discontinuation

For Parts 1 and 2, a summary of incidence rates (frequencies and percentages) of the participants with TEAEs leading to study drug discontinuation, by treatment group (treatment cohort for Part 2), SOC, and preferred term will be prepared. No inferential statistical tests will be performed.

A data listing of AEs leading to study drug discontinuation will also be provided, displaying details of the event(s) captured on the CRF.

9.2.2. Deaths and Serious Adverse Events

Any deaths that occur during the study will be listed.

Serious adverse events will be listed and also tabulated by system organ class and preferred term and presented by treatment group (treatment cohort for Part 2).

9.2.3. Other Significant Adverse Events

Adverse events of special interest (AESI) will be as collected on the CRF as a special interest event involving liver.

9.3. Clinical Laboratory Evaluations

For Part 1, descriptive statistics (n, mean, standard deviation [SD], median, minimum, and maximum) for clinical laboratory data and changes from baseline at each post-baseline time point will be presented by treatment group (treatment cohort for Part 2).

The baseline value is the last value observed prior to first administration of study drug and any information obtained after first administration of study drug is regarded as post-baseline information. The change-from-baseline variables will be calculated as the post-baseline value minus the value at baseline. Change from baseline on continuous data will be summarized using descriptive statistics at each post-baseline time point by treatment group. For categorical data, change from baseline will be summarized using frequency and proportion at each post-baseline timepoint by treatment group (treatment cohort for Part 2).

For all continuous clinical laboratory variables, a shift table comparing the baseline value (normal, low, and high) to the last observation on treatment will be presented by treatment group (treatment cohort for Part 2).

For urinalysis, a shift table (using number of participants with results of negative, trace, or positive) comparing the baseline value to the maximum value will be presented by treatment group (treatment cohort for Part 2).

For Part 2, descriptive statistics (n, mean, standard deviation [SD], median, minimum, and maximum) for clinical laboratory data and changes from baseline (last value observed during Follow-up Period I in Part 1) at each post-baseline time point will be presented for all participants for each scheduled time point.

For all continuous clinical laboratory variables in Part 2, a shift table comparing the baseline (last value observed during Follow-up Period I in Part 1) value (normal, low, and high) to the last observation on treatment will be presented for all participants.

For urinalysis in Part 2, a shift table comparing the baseline (last value observed during Followup Period I in Part 1) value to the maximum value will be presented for all participants (using number of participants with results of negative, trace, or positive).

Potentially clinically significant results of clinical laboratory evaluations identified using prospectively defined criteria (Table 3) will also be summarized descriptively by treatment group (treatment cohort for Part 2).

Lab Test Category	PCS Criteria
	Sodium: <132 mmol/L
	Sodium: >149 mmol/L
	Potassium:<2.5 mmol/L
	Potassium: >6.5 mmol/L
	Calcium: <1.62 mmol/L
Chemistry	Calcium:>3.49 mmol/L
	Uric acid:>715 µmol/L
	Albumin: <25 g/L
	eGFR: Decrease from baseline of ≥25%
	Glucose: ≤2.5 mmol/L
	Glucose:≥14.0 mmol/L
	Leukocytes: $\leq 2.5 \times 109/L$
	Leukocytes: $\geq 15.0 \ge 109/L$
	Neutrophils: $\leq 1.5 \ge 109/L$
Hematology	Platelets: $\leq 50.0 \text{ x } 109/\text{L}$
	Hemoglobin: Decrease from baseline of ≥ 20 g/L or ≤ 80 g/L (absolute value)
	Hematocrit: Decrease from baseline of \geq 10% (absolute change) or \leq 24% (absolute value)
Urinalysis	Glucose: ≥2+
	RBC/HPF: >10
	Protein: >2+
	Ketones: > 2 +
	Leukocytes: >10

Table 3: Potentially Clinically Important Criteria (PCS): Laboratory

For Part 1 and Part 2, individual data listings of clinical laboratory results will be presented for each participant. Values that meet laboratory PCS will be flagged in the clinical laboratory listings (see Table 3).

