8.13.1.2 Additional Liver Safety Analyses

The incidence of participants in Parts 1 and 2 who develop:

- >5 x-, 10 x-, and 20 x ULN elevations for ALT
- >3 x-, 5 x-, 10 x-, and 20 x ULN elevations for AST
- >3 x-, 5 x-, 10 x-, and 20 x ULN elevations for either ALT or AST
- Any elevation of bilirubin; elevated serum total bilirubin (TBL) to >2 x ULN
- Any elevation of alkaline phosphatase >1.5 x ULN
- Elevation of aminotransferase (>3 x ULN) accompanied by elevated bilirubin (>2 x ULN) and displayed as evaluation of Drug-Induced Serious Hepatotoxicity (eDISH) plots
- Elevation of aminotransferase in temporal association with nausea, vomiting, anorexia, abdominal pain, or fatigue
- Possible liver-related deaths and liver-related treatment discontinuations.

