8.13.3 Clinical Laboratory Tests

For Part 1, descriptive statistics (n, mean, standard deviation [SD], median, minimum, and maximum) for clinical laboratory data and changes from baseline at each post-baseline time point will be presented by treatment group.

The baseline value is the last value observed prior to first administration of study drug and any information obtained after first administration of study drug is regarded as post-baseline information. The change-from-baseline variables will be calculated as the post-baseline value minus the value at baseline. Change from baseline on continuous data will be summarized using descriptive statistics at each post-baseline time point by treatment group. For categorical data, change from baseline will be summarized using frequency and proportion at each post-baseline timepoint by treatment group.

For all continuous clinical laboratory variables, a shift table comparing the baseline value (normal, low, and high) to the last observation on treatment will be presented by treatment group.

For urinalysis, a shift table comparing the baseline value to the maximum value will be presented by treatment group (using number of participants with results of negative, trace, or positive).

For Part 2, descriptive statistics (n, mean, standard deviation [SD], median, minimum, and maximum) for clinical laboratory data and changes from baseline (last value observed during Follow-up Period I in Part 1) at each post-baseline time point will be presented for all participants for each scheduled time point.

For all continuous clinical laboratory variables in Part 2, a shift table comparing the baseline (last value observed during Follow-up Period I in Part 1) value (normal, low, and high) to the last observation on treatment will be presented for all participants.

For urinalysis in Part 2, a shift table comparing the baseline (last value observed during Follow-up Period I in Part 1) value to the maximum value will be presented for all participants (using number of participants with results of negative, trace, or positive).

For Part 1 and Part 2, individual data listings of clinical laboratory results will be presented for each participant. Values outside of the clinical laboratory's reference range (i.e., those with low or high values) will be flagged in the clinical laboratory listings.

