2.1.2. Key Safety Objective

To compare the incidences of liver chemistry test elevations in participants randomized to lixivaptan with participants randomized to placebo.

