9.3.1. Special Liver Events

For Part 1 and 2, summarizes using incidence (rates) for participants with special liver events will be presented for all participants by treatment group (treatment cohort for Part 2) for the following:

- ALT > 5 x, 10 x, or 20 x ULN
- AST > 3 x, 5 x, 10 x, or 20 x ULN
- ALT or AST > 3 x, 5 x, 10 x, or 20 x ULN
- Total Bilirubin $> 2 \times ULN$
- Alkaline phosphatase >1.5 x ULN
- Hy's Law (ALT > 3 x ULN and Total Bilirubin > 2 x ULN)
- Elevation of aminotransferase in temporal association with nausea, vomiting, anorexia, abdominal pain, or fatigue
- Possible liver-related deaths and liver-related treatment discontinuations

A time to first event analysis will also be presented using Kaplan-Meier product-limit estimates by treatment group for ALT > 3 x, AST > 3 x, ALT or AST > 3 x, and Total Bilirubin > 2 x ULN.

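### Mild, transient liver-test and sodium abnormalities are counted by participant only in a last-value shift table, and the SAP drops the protocol's any-elevation bilirubin row without recording it

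*SAP*

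**What the plan says.** The key safety objective in SAP 2.1.2 is broad: "To compare the incidences of liver chemistry test elevations" between the randomized arms. Its endpoint is narrower: ALT above 3 x ULN (protocol 2.2.1.2, SAP 4.1.4.1).

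For continuous laboratory variables SAP 9.3 plans "a shift table comparing the baseline value (normal, low, and high) to the last observation on treatment", in Part 1 and again in Part 2. The wording comes from protocol 8.13.3, which has "a shift table comparing the baseline value (normal, low, and high) to the last observation on treatment will be presented by treatment group". For urinalysis the same SAP section takes the worst value instead, "comparing the baseline value to the maximum value will be presented by treatment group".

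On bilirubin, protocol 8.13.1.2 lists two levels: "Any elevation of bilirubin; elevated serum total bilirubin (TBL) to >2 x ULN". SAP 9.3.1 keeps only the row above 2 x ULN. SAP 15, which is meant to record departures from the protocol, has no entry for this.

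On listings, protocol 8.13.3 flags every value outside the reference range. SAP 9.3 flags only values meeting Table 3. That table covers sodium, potassium, calcium, uric acid, albumin, eGFR, glucose, haematology and urinalysis, but not ALT, AST, bilirubin or alkaline phosphatase. SAP 15 does not record this change either.

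**The concern.** A shift table answers how many participants moved from normal to abnormal. If it uses the last on-treatment value, it answers only how many were abnormal at the end. A rise at month 3 that has settled by Week 52 is shown as normal to normal.

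The protocol makes such a pattern plausible. Section 7.3.7.1 says that dosing generally continues, with more frequent testing, when aminotransferases are at or below 3 x ULN or bilirubin is at or below 2 x ULN. Section 7.3.7.1.2 shows that the protocol does not ignore smaller rises: from 1.2 x ULN during run-in and titration they already call for discussion with the medical monitor. Sodium sampling was extended to strengthen safety monitoring, and mild sodium elevation is described as a known effect of the drug class (protocol 7.3.5).

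At stake is how fully the report describes low-grade liver and sodium changes, in a programme whose rationale is a better liver profile than tolvaptan's.

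**Working it through.** No figure in the plan needs reproducing. The check sets each analyte range against the outputs that could count participants in it.

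**Which outputs count whom**

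- ALT or AST above 3 x ULN: incidence (SAP 9.1 and 9.3.1) and Kaplan-Meier time to first event (9.3.1, repeated in 9.6). Independent of the last value.
- Bilirubin above 2 x ULN: incidence and Kaplan-Meier (9.3.1, 9.6). Independent of the last value.
- Alkaline phosphatase above 1.5 x ULN, and ALT above 3 x with bilirubin above 2 x ULN: incidence (9.3.1). Independent of the last value.
- Aminotransferase elevation accompanied by nausea, vomiting, anorexia, abdominal pain or fatigue: incidence, with no ULN multiple stated (9.3.1). This covers symptomatic mild rises.
- Sodium below 132 or above 149 mmol/L: Table 3 summary (9.3).
- ALT or AST above ULN up to 3 x ULN without those symptoms: shift table only.
- Bilirubin above ULN up to 2 x ULN: shift table only, because the any-elevation row is gone.
- Sodium out of range but within 132 to 149 mmol/L: shift table only.

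**Whether other displays fill the gap**

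- By-visit statistics (9.3) include a minimum and maximum for each arm and visit. That is one extreme, not a number of participants. Under SAP 6.1.5 an unscheduled result enters only if the scheduled one is missing and the date falls in the window, so most of the extra tests foreseen in protocol 7.3.7.1 stay out.
- The eDISH plot (9.1) is planned for Part 1 and gives no count.
- Listings hold every value, but a bilirubin of 1.8 x ULN carries no flag under SAP 9.3.

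**Illustration of what a last-value table misses**

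Inputs: liver chemistry and sodium are drawn at Visits 10 to 22, which is 22 − 10 + 1 = 13 visits (protocol Table 3 and 6.4). Assume a completer with no missing visit and an excursion covering d consecutive visits, with all positions equally likely. There are 13 − d + 1 = 14 − d positions, of which one includes Visit 22, so

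P(missed) = 1 − 1/(14 − d)

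- d = 1: 1 − 1/13 = 92.3%
- d = 2: 1 − 1/12 = 91.7%
- d = 3: 1 − 1/11 = 90.9%
- d = 6: 1 − 1/8 = 87.5%

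A worst-value table misses none of the excursions seen at a sampled visit. The full chemistry panel, drawn only at Visits 12, 15, 18 and 22, would give 1 − 1/4 = 75% for a single draw. That figure does not apply to liver tests or sodium, which are drawn at every visit.

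**The case against.** The case for leaving the plan alone has weight. The key safety endpoint is untouched: it counts participants who develop ALT above 3 x ULN at any time, with Fisher's exact test. The SAP did not invent the last-value comparator; it carried over the protocol's text. Urinalysis is a weak precedent, since negative/trace/positive has one adverse direction while sodium can be abnormal either way. Protocol 7.3.7.1 notes that lesser liver-test rises may reflect background variability in ADPKD. Abnormal results that the investigator judges clinically significant become adverse events and reach the TEAE tables. A participant who stops drug soon after an abnormality may have it as the last on-treatment value, which the completer arithmetic ignores.

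Most of this stands, and it rules out the stronger reading. A reader might infer that transient liver and sodium abnormalities vanish from the report, or that the shift table is the only place that could show them. The documents do not support that: threshold incidences, Kaplan-Meier curves, the eDISH plot, symptomatic aminotransferase rises, by-visit maxima and full listings are all independent of the last value.

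What the objection does not supply is a participant count for the mild range. Adverse-event reporting depends on clinical judgement, by-visit extremes are not counts, and the listing flags have been narrowed to exclude liver tests. Two adverse directions call for showing the highest and lowest values separately; they do not justify using the last one.

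**Conclusion.** The point holds for mild, transient abnormalities. For these, the only participant-level tabulation by a laboratory criterion is a shift table that classes a resolved abnormality as normal. The missing any-elevation bilirubin row and the narrower listing flags are departures from protocol 8.13.1.2 and 8.13.3 that SAP 15 does not record.

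The size cannot be given in participants, because the documents state neither the frequency nor the duration of such excursions. The 92% is illustrative and rests on 13 complete visits, a uniform position and completers. The conclusion also assumes that the Table 3 summary counts any post-baseline value, which SAP 9.3 does not state outright.

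This is a worthwhile improvement to the plan as written, with no effect on the key safety endpoint. Its consequence for this report is small: SAP 12 records that 5 participants were randomized, that no statistical analyses will be performed, and that limited tables and listings will be produced. The listing flags are therefore the part most likely to matter still.

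**What to change.** In SAP 9.3, for Part 1 and Part 2, present the shift from baseline to the worst on-treatment value, with highest and lowest shown separately and unscheduled results included, in place of or beside the last-value shift. In SAP 9.3.1, restore an incidence row for any bilirubin above ULN. In the laboratory listings, flag all values outside the reference range, as protocol 8.13.3 states. State that the Table 3 summary counts any post-baseline value.

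Protocol 8.14 lets the SAP modify the protocol's analysis plans, so an entry in SAP 15 for the new shift table is enough and no protocol amendment is needed. The cost is table-shell wording, one added row and a listing rule. Abnormal-shift frequencies will look higher in both arms, because each participant is judged on all draws rather than one; a footnote should say so.

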9.3.1. Special Liver Events

For Part 1 and 2, summarizes using incidence (rates) for participants with special liver events will be presented for all participants by treatment group (treatment cohort for Part 2) for the following:

- ALT > 5 x, 10 x, or 20 x ULN
- AST > 3 x, 5 x, 10 x, or 20 x ULN
- ALT or AST > 3 x, 5 x, 10 x, or 20 x ULN
- Total Bilirubin $> 2 \times ULN$
- Alkaline phosphatase >1.5 x ULN
- Hy's Law (ALT > 3 x ULN and Total Bilirubin > 2 x ULN)
- Elevation of aminotransferase in temporal association with nausea, vomiting, anorexia, abdominal pain, or fatigue
- Possible liver-related deaths and liver-related treatment discontinuations

A time to first event analysis will also be presented using Kaplan-Meier product-limit estimates by treatment group for ALT > 3 x, AST > 3 x, ALT or AST > 3 x, and Total Bilirubin > 2 x ULN.

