7.3.7 Assessment of Liver Symptoms, Signs, or Test Abnormalities

Testing for hepatic aminotransferases (ALT/AST), alkaline phosphatase, and total bilirubin will be performed at the timepoints as specified in the [Schedule of Procedures – Part 1](#) and [Schedule of Procedures – Part 2](#). Management of hepatic and liver chemistry test abnormalities are discussed below. *The appearance of any suspicious symptoms or signs of liver dysfunction as described in Appendix 2 (Section 13.2) in a participant at any time during the study should trigger prompt testing of liver chemistry tests (i.e., within 48 hours).*

7.3.7.1 Management of Liver Chemistry Test Abnormalities and Signs or Symptoms of Liver Dysfunction Occurring During Study Treatment

Elevations of liver aminotransferase levels >3 x ULN or total bilirubin levels >2 x ULN should prompt immediate retesting within 48 hours. Although central laboratory testing is preferred, local laboratory testing is acceptable, ideally with a concurrent central laboratory sample for confirmation. After the Investigator consults with the medical monitor and sponsor, temporary reduction in dose or interruption of study drug administration must be instituted if liver aminotransferase levels >3 x ULN or total bilirubin levels >2 x ULN are observed during the Lixivaptan Titration or Double-Blind Randomized Treatment Periods of Part 1 or the Lixivaptan Re-Titration or Maintenance Treatment Periods of Part 2. During the time that values remain elevated, testing should be done at least weekly for the first month, gradually returning to monthly as indicated by the results. In the presence of such liver chemistry test abnormalities, additional clinical testing (examples listed in Appendix 3 ([Section 13.3](#))) may be recommended by the medical monitor and sponsor and those results reported according to local guidelines.

Similarly, the appearance of any suspicious symptom or sign of liver dysfunction (see Appendix 2 ([Section 13.2](#))) at any time during the study should trigger prompt testing of liver chemistry (i.e., within 48 hours) and consultation with the medical monitor and sponsor to discuss any changes to dosing with study drug.

All elevations meeting these thresholds or confirmed symptoms or signs of liver dysfunction will be assessed for causality by an independent, blinded Hepatic Events Review Committee (HERC) (see [Section 7.3.7.2](#)).

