In the case of study drug interruption, re-starting study drug should be encouraged (see [except under these circumstances](#) below) after discussion with the medical monitor and sponsor, when liver chemistry tests have normalized or stabilized, and in conjunction with a plan for increased frequency of liver chemistry test monitoring.

Treatment with study drug cannot be resumed in participants when:

- aminotransferase levels $>8 \times$ ULN at any time,
- aminotransferase levels $>5 \times$ ULN for more than 2 weeks, or
- concurrent elevations of aminotransferase levels $>3 \times$ ULN and total bilirubin $>2 \times$ ULN

except under these circumstances:

Participants with these levels of abnormality may be re-challenged with study drug if abnormalities were adjudicated by the HERC as having a $\leq 50\%$ likelihood of being related to study drug (per DILI Network [DILIN] probability criteria, modified, Appendix 4 ([Section 13.4](#)) ([Fontana et al, 2009](#)) and the Investigator, medical monitor, and sponsor agree to an intensive monitoring plan to mitigate risk. The participant must also be willing to comply with these monitoring measures, be informed of the potential risks, and agree to study drug re-challenge.

Liver chemistry test increases of a lesser extent (serum aminotransferase levels $\leq 3 \times$ ULN or total bilirubin $\leq 2 \times$ ULN) will be discussed with the medical monitor. They may be related to the underlying variability of such test results in ADPKD patients ([Watkins et al, 2015](#)). Generally, dosing should continue during such lesser liver chemistry test increases; however, the frequency of laboratory testing should increase, particularly during the Double-Blind Randomized Treatment Period in Part 1 and the Maintenance Treatment Period in Part 2. Slowing of titration may also be considered if the abnormalities occur during the Lixivaptan Titration Period in Part 1 or Lixivaptan Re-Titration Period in Part 2.

For participants exhibiting an increase during the Lixivaptan Titration or Lixivaptan Re-titration Periods, follow the instructions in [Section 7.3.7.1.2 \(Liver Test Abnormalities during the Placebo Run-in and/or Lixivaptan Titration Period\)](#).

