7.3.7.2 Hepatic Events Review Committee (HERC) – Special Reporting of Liver Events

In order to adequately characterize the liver safety profile of lixivaptan, additional testing and data collection will be required for any participant who develops clinically significant liver chemistry test abnormalities and/or signs or symptoms of liver dysfunction during the study. This additional data will be reported on a liver dysfunction details eCRF. The type of information needed to complete it is provided in Appendix 2 ([Section 13.2](#)). The purpose of the liver dysfunction details eCRF and additional testing is to facilitate review and adjudication of each event of clinically significant liver chemistry test abnormalities and/or signs or symptoms of liver dysfunction during the study to determine the probable cause(s) of these abnormalities. The review and adjudication will be performed by an independent, blinded HERC, a committee of 3 to 4 experts experienced in liver disease. The HERC will use the modified DILIN probability criteria (0 to 5% = unrelated; 6 to 25% = unlikely, 25% to 50% = possibly, 51% to 75% = probably, 76% to 95% = very likely, >95% = definite; see [Appendix 4: DILI Network Causality Criteria, modified](#)) to assign attribution to each case of potential liver dysfunction. The HERC will independently decide attribution and will communicate in writing with the sponsor and the IDMC. The IDMC reviews data at a study-level and, as such, its recommendations will not be made known to the HERC so as not to bias the HERC when adjudicating participant cases. These two committees are independent and will have a one-way line of communication from HERC to IDMC. The results of the HERC review and adjudication will be incorporated into the reporting of the safety results of the trial. The result of these analyses may be presented separately from the final clinical study report (CSR).

The Investigator must complete and submit a copy of the liver dysfunction details eCRF with the SAE/AESI form within 24 hours of awareness through the SAE reporting pathway (described in [Section 7.3.8.3](#)) for any participant who develops an Adverse Event of Special Interest (AESI) related to abnormal liver chemistry test results or clinical signs or symptoms. Specifically, any participant who

- develops ALT or AST levels $>3 \times \text{ULN}$,

- develops total bilirubin levels $>2 \times$ ULN,

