9.1. Key Liver Safety Analysis

The incidence of participants who develop serum ALT levels >3 x ULN will be summarized by treatment group for Part 1 and by treatment cohort for Part 2. For Part 1, Fisher's exact test will be used to test if the incidence rate in the lixivaptan group is different from that in the placebo group.

In addition, an eDISH plot will be presented for Part 1.

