This study has been early terminated by the Sponsor. Due to only 5 participants being randomized into double-blinded, randomized treatment period in Part 1 and all being prematurely terminated in Part 1 of the study, no statistical analyses will be performed and only a limited set of summary tables will be generated along with the study data listings to facilitate the creation of a synoptic clinical study report.

13. Tables, Listings, and Figures

All listings, tables, and figures will have

- A header showing the sponsor company name, protocol, and page number
- A footer showing the file name and path, the source of the data (ADaM dataset or listing number) and date/time created.

The layouts of tables, listings, and figures are presented in SAP Mock Tables, Listings and Figures. These layouts incorporate all the appropriate table titles, table numbers, and footnotes.

14. Mock Tables, Listings, and Figures

The table, listing, and figure shells will be provided in a separate document.

15. Changes from Protocol

Any analyses that deviated from the study protocol are documented below.

Text in Protocol	Change in SAP	Justification
None	Placebo Run-in Safety Set, Lixivaptan Titration Safety Set, ITT, mITT, PPAS, Lixivaptan Treated Safety Set are added in Section 5 Analysis Population	Those analyses population will be needed to summarize the efficacy or safety data
Analysis safety and efficacy sets for Part 2 in Section 5 Analysis Populations	Re-define as two analysis sets: P2SS for safety and P2EAS efficacy, but summary in Part 2 will be presented by treatment cohort	The revised analysis populations are more appropriate for safety and efficacy analyses in Part 2.
LV for analysis	htLV for analysis	To reduce the variance of LV and normalize to participant's height
Annualized change from baseline in htTKV (htLV)	Annualized percent change from baseline in htTKV (htLV)	Anti-log of annualized change from baseline based on the log- transformed htTKV (htLV) implies the annualized ratio of htTKV (htLV) at the evaluated timepoint to baseline htTKV (htLV). This ratio minus one as expressed as percentage will represent annualized percent change from baseline in htTKV (htLV), but not annualized change from baseline in htTKV (htLV).
None	Lixivaptan treated safety summaries have been added in Section 9.6	To add overall safety after randomization during the entire study for all lixivaptan-treated participants during double-bind phase and/or open-label phase.

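### SAP 9.3.1 bases its only combined liver-injury row on ALT alone, whereas protocol 8.13.1.2 counts ALT or AST, and SAP Section 15 does not record the change

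*SAP*

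**What the plan says.** Protocol 8.13.1.2 lists liver events whose incidence is to be reported in Parts 1 and 2. One of them is "Elevation of aminotransferase (>3 x ULN) accompanied by elevated bilirubin (>2 x ULN"), with eDISH plots as its display. Protocol 7.3.7 shows which enzymes are meant: "Testing for hepatic aminotransferases (ALT/AST), alkaline phosphatase, and total bilirubin". Protocol 7.3.7.2 also treats the two enzymes alike, since special liver reporting applies to anyone who "develops ALT or AST levels" above 3 times ULN.

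SAP 9.3.1 gives the corresponding list for both Parts. It has rows for ALT, for AST, for either enzyme ("ALT or AST > 3 x, 5 x, 10 x, or 20 x ULN") and for total bilirubin above 2 times ULN. Its one row joining an enzyme to bilirubin is headed Hy's "Law (ALT > 3 x ULN and Total Bilirubin > 2 x ULN"). SAP 9.1 adds: "In addition, an eDISH plot will be presented for Part 1". SAP 9.6, the pooled lixivaptan summary, repeats the separate thresholds and has no combined event.

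SAP Section 15 opens with the statement "Any analyses that deviated from the study protocol are documented below". Its table has no entry for the combined liver criterion.

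**The concern.** Anyone who programs the SAP as written will produce a narrower event than the protocol plans, and nothing in the SAP warns a reader of the difference. The separate rows do not make up for it. They show how many participants crossed each threshold, but not how many crossed both.

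The combined row matters more here than in most programmes. Protocol 1.9 describes determining the risk of drug-induced liver injury as one of the study's two primary objectives, and the case for the drug rests on less liver toxicity than tolvaptan. The combined event is expected to be rare, so a definition that can leave out a case deserves correction even if few cases are affected.

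**Working it through.** The plan gives no figure for this event, so there is nothing to reproduce. The check compares the two definitions.

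**Step 1. The rules.** Values are multiples of ULN; TBL is total bilirubin.

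- Protocol (8.13.1.2 read with 7.3.7): (ALT > 3 or AST > 3) and TBL > 2.
- SAP (9.3.1): ALT > 3 and TBL > 2.

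The protocol's combined item says bilirubin without the word total. I read it as total bilirubin because the neighbouring item in the same list and the rules in 7.3.7.1 apply the 2 times limit to total bilirubin.

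**Step 2. Test cases.**

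| ALT | AST | TBL | Protocol | SAP |
|---|---|---|---|---|
| 4 | 4 | 2.5 | counted | counted |
| 4 | 2 | 2.5 | counted | counted |
| 2.5 | 4 | 2.5 | counted | **not counted** |
| 2.5 | 4 | 1.5 | not counted | not counted |

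**Step 3. The difference.** Every participant who meets the SAP rule also meets the protocol rule. The participants left out are exactly those with AST > 3, ALT ≤ 3 and TBL > 2. On the choice of enzyme, the SAP count can equal the protocol count or fall below it, but cannot exceed it.

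**Step 4. Scale.** The documents give no rate for AST-only cases, so I assume 0, 1 or 2 among the 900 participants planned for lixivaptan in Part 1 (SAP 3.7). The exact one-sided 95% upper bound is 1 − 0.05^(1/900) for no cases. For x cases it is the 95th percentile of a Beta(x + 1, 900 − x) distribution.

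| Cases | Proportion | Upper bound |
|---|---|---|
| 0 | 0% | 0.33% |
| 1 | 1/900 = 0.11% | 0.53% |
| 2 | 2/900 = 0.22% | 0.70% |

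The SAP does not plan to report such a bound, and Part 2 would have a different denominator. The table shows scale only.

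**Step 5. Other places where the case would show.** An omitted participant is counted in the AST row, the either-enzyme row and the bilirubin row, and in the matching Kaplan-Meier analyses (SAP 9.3.1). The values are in the individual laboratory listings (SAP 9.3). Both elevations trigger special liver reporting and blinded causality review (protocol 7.3.7.1 and 7.3.7.2). None of these is a tabulated combined count.

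**Step 6. eDISH.** The protocol attaches the display to the combined event in Parts 1 and 2. The SAP plans it for Part 1 only and does not name the aminotransferase axis.

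**The case against.** Four points can fairly be made for the SAP.

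- **An ALT focus is consistent with the trial.** The key liver endpoint is ALT above 3 times ULN, and Fisher's exact test is planned for that endpoint alone (SAP 9.1). This explains the row, but the protocol's separate combined event still includes AST.
- **The SAP is allowed to differ.** Protocol 8.14 lets the SAP modify the protocol's plans and asks for an amendment only for major changes to the primary analysis. The narrowing is therefore permitted. Leaving it out of Section 15 is not consistent with that section's own statement.
- **No data are lost.** This stands, for the reasons in Step 5. Liver management and hepatic review follow the protocol and do not depend on a SAP table row. However, a reader would have to find co-occurring elevations by inspecting listings, and the flagging criteria in SAP Table 3 contain no ALT, AST or bilirubin limit.
- **The trial ended early.** SAP Section 12 says 5 participants were randomized and no statistical analyses will be performed. This removes most of the practical effect but does not make the two definitions agree.

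A reader might also infer that the SAP dropped a timing requirement, so that ALT and bilirubin peaks months apart would now count. The documents do not support this. The phrase "concurrent elevations of aminotransferase levels" comes from the rule on resuming study drug in protocol 7.3.7.1, which is not an analysis definition. The analysis item in 8.13.1.2 says only that one elevation is accompanied by the other and sets no window. The SAP row sets none either, so no stated window was removed.

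**Conclusion.** The concern holds as a mismatch of definition. SAP 9.3.1 is narrower than protocol 8.13.1.2, the change is unrecorded, and participants with AST above 3, ALT at or below 3 and bilirubin above 2 times ULN drop out of the only combined count. The Part 1 restriction on the eDISH plot is a second, smaller departure from the same protocol item.

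The number affected is unknown and probably small. The 0.11% per case in Step 4 rests on an assumed count and the planned Part 1 arm.

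Two further inferences should not be drawn. One is that a missed case would change the trial's liver conclusion. No test, threshold or interval is attached to this row, so the documents give no basis for that. The other is that the eDISH plot is itself ALT-only. The SAP does not name its axis, so this cannot be shown.

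**What to change.** In SAP 9.3.1, define the combined row as (ALT or AST) above 3 times ULN accompanied by total bilirubin above 2 times ULN, for Parts 1 and 2. An ALT-only Hy's Law row can be kept beside it. In SAP 9.1, present the eDISH display for both Parts and name the aminotransferase axis. If the ALT-only definition is intended, enter it in Section 15 with a reason.

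Stating a time window for the two elevations would help programming and reading. It would be new text for this analysis, because neither document gives one.

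The cost is about one line of SAP text with the matching code for the row, plus a repeat of the eDISH figure for Part 2. The enzyme and bilirubin measurements are already in the schedule for both Parts, so no new data are needed.
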